7.8.2. Creation of Analytic Cohorts and Source Data Characteristics

A flow diagram will be provided to reflect the order of operations used to create the analytic cohort from the source database. Temporality of assessment windows will be provided relative to the cohort entry (index date) including additional data to denote exclusion/inclusion criteria and how the final sample was derived.

A table about the source of data (pharmacy claims, medical claims, enhanced hospital claims) will be provided. The table will include calendar time cohort entry (index date) and calendar time range of available data in the pre-index and post-index assessment windows.

7.8.3. Analysis Populations

Analysis population are all patients meeting the study inclusion/exclusion criteria and selected after propensity matching. The same matched population will used for both effectiveness and safety analysis.

The effectiveness evaluation will be conducted using an ITT analysis, meaning that the first fracture event during the 18 months (+ 30 days follow-up) after the index date will be summarized regardless of when treatment ended. Cardiovascular safety outcomes will be evaluated using an As-Treated (AT) analysis based on only events occurring during the treatment period which is from the index date to the last prescription anabolic drug obtained within the 18 months after the index date, regardless of the anabolic drug possession gap between any 2 prescription fills.

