2. PROTOCOL SYNOPSIS

Title:

A Retrospective, Observational Cohort Study Evaluating the Effectiveness and Cardiovascular Safety of Abaloparatide in Postmenopausal Women New to Anabolic Therapies

Name of Sponsor:

Radius Health, Inc. (Radius)

Reference Drug:

Teriparatide subcutaneous (TPTD; Forteo[®])

Background and Rationale:

Osteoporosis is a highly prevalent systemic skeletal disorder characterized by compromised bone strength predisposing individuals to an increased risk of fractures. Anabolic drugs, which can add bone and potentially improve bone microarchitecture, have become available as an additional treatment options for individuals with osteoporosis. These anabolic drugs include teriparatide (TPTD; Forteo: Eli Lilly and Co., Indianapolis, IN, USA), a first-in-class anabolic agent that received United States of America (USA) Food and Drug Administration (FDA) approval in 2002, abaloparatide (ABL; TYMLOS: Radius Health, Inc., Boston, MA, USA), approved by the FDA in 2017 and romosozumab (Romo; Evenity: Amgen and UCB, Thousand Oaks, CA, USA), a humanized monoclonal antibody with dual action approved by the FDA in 2019. The FDA approval of ABL included consideration of results at 18 months from the landmark ACTIVE trial and the first 6 months of the ACTIVExtend trial, which demonstrated consistent significant and rapid reductions in the risk of vertebral and nonvertebral fractures regardless of age, years since menopause, presence or absence of previous fracture, and bone mineral density (BMD).

Research Question:

The purpose of the current study is to evaluate the real-world comparative effectiveness and cardiovascular safety of ABL compared with TPTD during the 18-month period after treatment initiation in propensity score (PS)-matched cohorts.

Objectives and Endpoints:

Objectives	Endpoints
Primary Objective: 
 To evaluate the effectiveness of ABL for the treatment of osteoporosis in postmenopausal women in the real-world healthcare setting in the USA compared with TPTD using the same cohort of PS-matched patients. 	Primary Endpoint: 
 Time to the first incidence of nonvertebral fracture (hip, pelvis, shoulder, radius or ulna, wrist, femur, tibia or fibula, ankle) within the 18 months after treatment initiation.

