5. RESEARCH QUESTIONS, OBJECTIVES, AND ENDPOINTS

5.1. Research Questions

The purpose of the current study is to evaluate the real-world effectiveness and cardiovascular safety of abaloparatide (ABL) compared with teriparatide (TPTD) for the treatment of osteoporosis in postmenopausal women during the 18-month period after treatment initiation in propensity score (PS)matched cohorts.

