5.2. Objectives and Endpoints

Objectives	Endpoints

Primary Objective:
 
 • To evaluate the effectiveness of ABL for the treatment of osteoporosis in postmenopausal women in the real-world healthcare setting in the United States of America (USA) compared with TPTD using the same cohort of propensity score (PS)-matched patients. 	
Primary Endpoint:
 
 • Time to the first incidence of nonvertebral fracture (hip, pelvis, shoulder, radius or ulna, wrist, femur, tibia or fibula, ankle) within the 18 months after treatment initiation.

Secondary Objective:
 
 • To evaluate the cardiovascular safety of ABL for the treatment of osteoporosis in postmenopausal women in the real-world healthcare setting in the USA compared with TPTD using the same cohort of PS-matched patients. 	
Secondary Endpoints:
 
 • Time to the first incidence of the composite endpoint of nonfatal MI, nonfatal stroke, or in-hospital cardiovascular death within the 18 months after treatment initiation and while still on therapy. • Time to the first incidence of the composite endpoint of nonfatal MI, nonfatal stroke, heart failure or in-hospital cardiovascular death within the 18 months after treatment initiation and while still on therapy.

Exploratory Objective:
 
 • To further evaluate the effectiveness and cardiovascular safety of ABL for the treatment of osteoporosis in postmenopausal women in the real-world healthcare setting in the USA compared with TPTD using the same cohort of PS-matched patients. 	
Exploratory Endpoints:
 
Efficacy
 
 • Time to the first incidence of hip fracture within the 18 months after treatment initiation. 
Safety
 
 • Time to the first incidence of MI • Time to the first incidence of stroke • Time to the first incidence of in-hospital cardiovascular death • Time to the first incidence of heart failure

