6.2.3. Abaloparatide

Abaloparatide is a chemically synthesized analog of the first 34 amino acids of human parathyroid hormone-related peptide [hPTHrP(1-34)] that is anabolic in bone. Secondary pharmacological effects of ABL include transient and reversible increases in heart rate after injection, with associated AEs of palpitations and tachycardia observed in the pivotal clinical study. A post-hoc analysis was performed to examine the effects of treatment on heart rate, blood pressure, and cardiovascular-related AEs, including MACE with or without heart failure in the ACTIVE/ACTIVExtend study ([Cosman et al, 2020](#)). ABL and TPTD transiently increased heart rate relative to placebo. After the first dose, the mean (SD) change in heart rate from before treatment to 1 hour after treatment was 7.9 (8.5) bpm for ABL, 5.3 (7.5) bpm for TPTD, and 1.2 (7.1) bpm for placebo. A similar pattern was observed over subsequent visits. The corresponding change in mean supine systolic and diastolic blood pressure 1 hour after treatment was -2.7/-3.6 mmHg for ABL, -2.0/-3.6 mmHg for TPTD, and -1.5/-2.3 mmHg for placebo. The percentage of participants with serious cardiac AEs was similar across the treatment groups (0.9% and 1.0%). In a post-hoc analysis, the percentage of participants with MACE during the ACTIVE study was 0.5% in the ABL group, 0.6% in the TPTD group, and 1.2% in the placebo group; MACE + heart failure increased the proportion in the placebo group to 1.7%. Time-to-first incidence of MACE + heart failure was significantly longer for ABL compared with placebo ($p = 0.02$) and for TPTD compared with placebo ($p = 0.04$; [Cosman et al, 2020](#)). During the 2-year ACTIVExtend period, the incidence of MACE, with or without heart failure, was similar between the placebo/alendronate and ABL/alendronate groups leading to the conclusion that ABL was associated with transient increases in heart rate and small decreases in blood pressure in postmenopausal women with osteoporosis, with no increase in risk of serious cardiac AEs, MACE, or heart failure.

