7.6.7.2. Evaluation of Cardiovascular Safety

Evaluation of cardiovascular safety outcomes will be carried out for patients who have 18 months of follow-up data from their index date while on treatment with ABL or TPTD. The following data variables will be extracted:

- End of treatment date which is the last prescription date + supply day
- Date of the first incidence of MI
- Date of the first incidence of stroke
- Date of the first incidence of heart failure
- Date of in-hospital cardiovascular death
- Date of all-cause in-hospital death

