7.8.7. Safety Analyses

A Cox proportional hazards model will be used for the time to first cardiovascular event. HR and 95% CIs will be presented.

The ICD-10 diagnosis from the hospital claim and physician claim will be used to derive post-index myocardial infarction (MI) (I21.x, I22.x), stroke (I61.x – I63.x), or heart failure (I50.x, excluding I50.x2, I50.8x). Hospital discharge status code (20 to 29 or 40 to 42) will be derived for in-hospital death. A detailed code list is provided in [Appendix 3](#). Subjects with in-hospital cardiovascular death derived from indirect approach 2 ([Xie et al, 2018](#)) will be included in the analyses. 2018 ICD-10 CM and General Equivalence Mappings (GEMS) from the Centers for Medicare & Medicaid (CMS) ([will be used to translating ICD-9 CM to ICD-10 CM \(CMS, 2018\)](#)).

The As-Treated (AT) analysis will be conducted for the safety evaluation. The first incidence of a cardiovascular event after the index date and before the 30 days after the end of treatment will be analyzed.

A cardiovascular event is the first incidence of the composite endpoint of nonfatal MI, nonfatal stroke, or in-hospital cardiovascular death; the first incidence of the composite incidence of nonfatal MI, nonfatal stroke, heart failure or in-hospital cardiovascular death; or the first incidence of MI, stroke, heart failure, or in-hospital cardiovascular death separately.

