7.8.10.2. Safety Endpoints

All-cause in-hospital death without any restriction will replace in-hospital cardiovascular death as the sensitivity analysis on secondary safety endpoints.

The cardiovascular events (MI, stroke, and heart failure) in the secondary endpoint is the first post-index incidence recorded on a hospital claim or physician claim. To evaluate possible overestimation, new incident of MI, stroke, or heart failure as no previous diagnosis in the 183 days preceding the index date as in the Sentinel Initiative ([Cutrona et al, 2013](#)) will be carried as a sensitivity analysis.

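### Cardiovascular events are counted only on treatment (plus at most 30 days), and no sensitivity analysis follows women to 18 months after they stop

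*Combined protocol and SAP*

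**What the plan says.** Section 5.1 frames the comparison as "for the treatment of osteoporosis in postmenopausal women during the 18-month period after treatment initiation in propensity score (PS)matched cohorts". The synopsis likewise asks about "cardiovascular safety of ABL compared with TPTD during the 18-month period after treatment initiation". Neither restricts the question to time on drug. Under Evaluation Period, section 7.1 says that CV evaluation, like effectiveness evaluation, runs for 18 months from the index date.

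The secondary endpoints in section 5.2 are narrower: "in-hospital cardiovascular death within the 18 months after treatment initiation and while still on therapy". Section 7.1 (Primary Analyses) makes as-treated the primary safety analysis, and section 7.8.3 carries it out: "Cardiovascular safety outcomes will be evaluated using an As-Treated (AT) analysis based on only events occurring during the treatment period".

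The end of the CV window is given in three ways:
- Sections 7.6.7 and 7.8.3 stop at the last prescription within 18 months.
- Section 7.6.7.2 defines "End of treatment date which is the last prescription date + supply day".
- Section 7.8.7 allows a further month: "The first incidence of a cardiovascular event after the index date and before the 30 days after the end of treatment will be analyzed".

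The safety sensitivity analyses in 7.8.10.2 change the death component ("All-cause in-hospital death without any restriction will replace in-hospital cardiovascular death as the sensitivity analysis on secondary safety endpoints") or require no MI, stroke or heart failure diagnosis in the 183 days before index. Section 7.8.10.1 changes the caliper or excludes women by exposure or prior treatment. For fracture, 7.8.3 specifies an ITT analysis that keeps counting after treatment stops.

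**The concern.** The question and the analysis differ in scope. A woman who stops at month 2 and has an MI at month 6 falls within the question in section 5.1 but counts in no planned CV analysis.

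This matters if women who stop differ in CV risk and stop at different rates in the two arms. Section 6.2.3 gives a reason to consider that. It names palpitations and tachycardia as associated with ABL, and says the first-dose change in heart rate "was 7.9 (8.5) bpm for ABL, 5.3 (7.5) bpm for TPTD, and 1.2 (7.1) bpm for placebo". If symptomatic women are also at higher CV risk and stop ABL sooner than TPTD, censoring at stopping removes more high-risk time from the ABL arm and pulls the HR down. The variables listed in section 7.6 include no reason for stopping, so the as-treated result cannot be checked against this. Events after stopping are also lost, from an endpoint that is likely to be sparse.

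**Working it through.** The plan gives no power, event count or stopping rate for the CV endpoints, so there is no figure of its own to reproduce. Inputs from the documents: 8,000 women per arm (7.8.1.2); 18 months = 540 days (7.1); 30 days after end of treatment (7.8.7); MACE of 0.5% for ABL and 0.6% for TPTD in ACTIVE (6.2.3), average 0.55%. All stopping and risk-group inputs below are assumptions.

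**1. How much time one early stopper loses.** Take one fill with a 30-day supply (assumed). The window ends at day 0 (last fill), day 30 (fill plus supply) or day 60 (plus 30 days). Even the longest leaves 1 − 60/540 = 89% of her 18 months uncounted.

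**2. Are the data available?** Entry closes 30 June 2019 and data run to 31 January 2021 (Table 3). The last entrant reaches day 540 on 21 December 2020. Calendar time is sufficient.

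**3. Events lost.** With full follow-up, 16,000 × 0.0055 = 88 events. Let p be the share still on drug at 18 months, with exponential stopping at rate d = −ln(p)/540. Counting to end of treatment plus 30 days, capped at day 540, the share of person-time kept is [30 + (1 − exp(−510d))/d]/540. The expected upper 95% limit at a true HR of 1 is exp(1.96 × 2/√E) for E events.

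| p (assumed) | Time kept | Events at 0.55% | Upper limit | Events at 2% (assumed) |
|---|---|---|---|---|
| full follow-up | 100% | 88 | 1.52 | 320 |
| 70% | 86% | 75 | 1.57 | 275 |
| 50% | 75% | 66 | 1.62 | 240 |
| 30% | 62% | 55 | 1.70 | 199 |

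**4. Bias, mild scenario.** Suppose 10% of women have three times the CV rate, and half of these stop at once on ABL against a quarter on TPTD. Relative rates among those remaining are:
- ABL: (0.05 × 3 + 0.90)/0.95 = 1.105
- TPTD: (0.075 × 3 + 0.90)/0.975 = 1.154

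A true HR of 1 reads 1.105/1.154 = 0.96.

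**5. Bias, stronger scenario.** Suppose 15% of women have four times the hazard, overall 18-month risk is 2%, and 50% of the other women are on drug at 18 months in both arms. The as-treated HR is the b that solves the Cox score equation Σ n₁ = Σ (n₀ + n₁)·b·d₁/(d₀ + b·d₁), summed over days, where n and d are the event rate and the number at risk in each arm (0 = TPTD, 1 = ABL).

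| High-risk women on drug at 18 months: TPTD / ABL | True 1.00 reads | True 1.30 reads |
|---|---|---|
| 50% / 50% | 1.00 | 1.30 |
| 40% / 40% | 1.00 | 1.30 |
| 40% / 20% | 0.945 | 1.227 |
| 50% / 20% | 0.924 | 1.200 |
| 50% / 10% | 0.885 | 1.150 |

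Risk-related stopping that is equal in both arms leaves the HR unbiased. Only a difference between arms moves it.

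**The case against.** The on-therapy window is declared in the endpoint itself and is a normal primary choice for drug safety, since off-drug time dilutes an on-treatment effect. That stands, and the primary analysis should stay.

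A reader might infer that women who stop leave observation. They do not: they are censored, and their claims are still held. Gaps between fills are ignored, so only women with no later fill are cut off.

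A reader might also infer that the as-treated HR is biased in favour of ABL. The documents do not support that. They give no stopping rate and no reasons for stopping. Section 6.2.3 describes the heart-rate rise as transient and reports similar MACE in the two active arms, and section 6.2.1 lists palpitations as common with TPTD too. Nothing in the documents links these symptoms to MI or stroke.

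The illustrated shifts are also small against sampling error. With 55 to 75 events, SE(log HR) = 2/√E is 0.27 to 0.23, so the mild shift (ln 0.958 = −0.043) is under one-fifth of a standard error. In the stronger scenario with 240 events, ln 0.924 = −0.079 against 0.129 is about 0.6 of one.

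Finally, an 18-month analysis has weaknesses of its own. Medical claims are open and unadjudicated, with about 60% professional outpatient capture (7.5) and 60% inpatient capture (6.3), so time after stopping may be counted as event-free when it was not seen. Women who switch anabolic within 18 months are excluded (Table 2), and no analysis of this cohort recovers them. These points limit what the added analysis can show; they do not remove the reason for having it.

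**Conclusion.** The concern holds in a limited form. Section 5.1, the synopsis and the Evaluation Period text in 7.1 set an 18-month CV evaluation. The endpoints and all CV analysis sections count on-therapy events to at most 30 days after end of treatment, and no sensitivity analysis follows women further. It would go too far to call the endpoint wrong: the declared endpoint is analysed as declared, and it is the broader question that goes unanswered.

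Bias in the HR requires stopping that is both related to CV risk and different between arms. That is plausible from section 6.2.3 but undocumented, and its size cannot be derived from the plan; under the assumed inputs a true HR of 1.00 reads between 0.885 and 1.00. The loss of events does not depend on that mechanism: about 15% to 38% of 88 (13 to 33 events) at 70% to 30% persistence, which is also assumed. This is an inexpensive improvement to the plan and does not invalidate the primary safety analysis.

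**What to change.** 1. Keep the as-treated analysis as primary.
2. Add to 7.8.10.2 a prespecified sensitivity analysis of both CV composites in the same matched cohort, by index medication, from the index date to day 540 or in-hospital death, whether or not treatment has stopped. State 540 days explicitly, because the fracture window is itself inconsistent (18 months in 7.6.7.1; 18 months plus 30 days in 7.8.3).
3. Report its HR and 95% CI beside the as-treated result, with time to discontinuation and the proportion discontinuing by arm.
4. Reconcile the Evaluation Period text in 7.1 with 7.6.7, 7.8.3 and 7.8.7, and choose one window end from the three now given.
5. Attach no pass/fail rule to agreement between the two HRs. If the as-treated analysis shares 62% to 86% of the events (assumed), the two log HRs correlate at about the square root of that share, 0.79 to 0.93. At a true HR of 1 their directions then differ by chance with probability arccos(r)/π, which is 21% to 12%. The plan has no CV margin against which to judge an upper limit, and fewer events alone raise the as-treated limit.

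The cost is one further Cox model for each composite on data already extracted, plus a discontinuation table. State the downsides in the plan: dilution by off-drug time, possibly incomplete capture after stopping, and the exclusion of switchers.

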7. RESEARCH METHODS

7.1. Study Design

This will be a retrospective observational study using administrative data for the period from May 2012 to January 2021. The most recently available data at the time of data extraction will be used. This study will use anonymized patient claims data from PRA's Symphony Health Patient Source Integrated Dataverse (IDV) database with the inclusion of enhanced hospital data, which are claims and remittance from the inpatient hospital setting and proprietary Patient Transactional Dataset (PTD) claims and prescription data, to apply the inclusion/exclusion criteria for patient selection (see [Section 7.4.1](#)) to form the data set.

Figure 1 Study Design Schematic

ABL= abaloparatide; TPTD = teriparatide.

The **Identification Period** is the period of time during which subjects will be identified based on their index date (01 May 2017 to 30 June 2019).

The **Index Date** is the date on which the subject filed their first claim for a prescription for either ABL or TPTD during the identification period.

The **Pre-index Period** consists of the 5 years before the Index Date during which medical history was available for the subject.

The **Post-index Treatment Period** consists of the 18 months plus 30 days follow-up after the initiation of treatment with anabolic drug (ABL or TPTD) on the index date and continuing for the duration of treatment.

Treatment Cohorts

This is a real-world observational study. Treatments will not be assigned. Instead, cohorts are defined as follows:

- **Abaloparatide Cohort:** Patients who filled ≥ 1 prescription for ABL (TYMLOS) as their index medication during the identification period.

- **Teriparatide Cohort:** Patients who filled ≥ 1 prescription for TPTD (Forteo) as their index medication during the identification period.

Evaluation Period

The date of the first claim for either ABL or TPTD during the identification period (between May 1, 2017 and June 30, 2019) will be considered the index date.

- The medication received on the index date will be considered the index medication.
- Treatment duration may continue for up to 18 months (540 days) after the index date.
- The evaluation of outcomes will start immediately after treatment initiation and will continue for 18 months after the index date for both effectiveness and cardiovascular safety evaluation regardless of the drug possession gap between any 2 prescription fills.

Primary Analyses

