- The primary effectiveness analysis will be an Intention-to-Treat (ITT) analysis.
- The primary safety analysis will be an As-Treated (AT) analysis.

Estimated Sample Size

Between May 2017 and June 2019, a total of 16,482 unique female patients ≥ 50 years of age treated with ABL and 45,350 unique patients ≥ 50 years of age treated with TPTD have been identified in the Symphony database. After applying inclusion/exclusion criteria, the final number of patients will be determined through PS matching. Based on previous studies, it is estimated that approximately 8,000 matched patients will be included in each cohort.

[figure not shown]

[figure not shown]
Sponsor Name: Radius Health, Inc.

Protocol Number: BA058-05-028

Protocol Version and Date: Original, V1.0, dated 09 July 2021

Page 27 of 63

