7.6.7. Outcomes

Both effectiveness and cardiovascular safety outcomes will be assessed for patients with 18 months of follow-up data after their index date. Cardiovascular safety outcomes will be evaluated during the treatment period which is from index date to the last prescription anabolic drug possessed within the 18 months after the index date, regardless of the anabolic drug possession gap between any 2 prescription fills.

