7.8.8. Anabolic Drug Exposure

The overall duration of cohort anabolic drug exposure will be summarized for PS-matched patients.

Overall Duration of Anabolic Drug Exposure (day) = Date of last anabolic drug prescription fill + Supply days – index date + 1

Consecutive treatment duration is determined from the index date to the last drug supply date without any gap exceeding 60 days.

Because the efficacy and safety evaluations are limited to an 18-month period, the overall duration of the anabolic drug exposure will be cut off at 540 days, even if the patient used the anabolic drug (ABL or TPTD) for > 18 months.

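### The as-treated window for the cardiovascular endpoints has conflicting end dates, and no planned analysis ends it at a gap in supply

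*Combined protocol and SAP*

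**What the plan says.** Section 7.1 states that "The primary safety analysis will be an As-Treated (AT) analysis". The window for that analysis is described in several places:

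- 7.8.3 counts only events in "the treatment period which is from the index date to the last prescription anabolic drug obtained within the 18 months after the index date".
- 7.6.7 uses "the treatment period which is from index date to the last prescription anabolic drug possessed within the 18 months after the index date".
- 7.6.7.2 extracts an "End of treatment date which is the last prescription date + supply day".
- 7.8.7 adds a tail: "The first incidence of a cardiovascular event after the index date and before the 30 days after the end of treatment will be analyzed".
- 5.2 defines both secondary composites as events "within the 18 months after treatment initiation and while still on therapy".
- 7.1 (Evaluation Period) says that outcome evaluation "will continue for 18 months after the index date for both effectiveness and cardiovascular safety evaluation regardless of the drug possession gap".

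Section 7.8.8 says "the overall duration of the anabolic drug exposure will be cut off at 540 days", while 7.1 and 7.8.9 describe a period of 18 months plus 30 days. Both 7.6.7 and 7.8.3 disregard gaps between fills, whatever their length. A 60-day gap limit appears in 7.8.8, but only to define consecutive treatment duration. Censoring is written out for fractures (7.8.6) and not for CV events (7.8.7).

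**The concern.** CV safety is the secondary objective. If the window has several possible ends, two careful programmers can count different events and different person-time for the same woman and both claim to follow the plan.

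The gap rule raises a second issue. Whether a woman is treated during a gap is decided by something later, namely whether she fills again. A woman who dies in the gap cannot fill again, so her window closes at her last supply plus the tail and a later death is dropped. A woman who survives and refills contributes the whole gap as treated time. In-hospital CV death is a component of both secondary composites and an exploratory endpoint by itself, so its on-treatment frequency would be too low whenever long gaps occur.

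**Working it through.** **Calendar.** The plan sets 1 month = 30 days (7.8.6). 18 × 30 = 540 days, which reproduces the figure in 7.1. Adding the tail, 540 + 30 = 570 days, the 19 months of 7.8.6.

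**End dates.** Days' supply is not given; 30 days is assumed.

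| Rule | One fill, day 0 | Monthly fills to day 510 |
|---|---|---|
| 7.6.7.2 + 7.8.7 (supply + 30) | 0 + 30 + 30 = 60 | 510 + 30 + 30 = 570 |
| No tail (5.2, using the 7.6.7.2 end date) | 0 + 30 = 30 | 510 + 30 = 540 |
| 7.1, fixed 18 months | 540 | 540 |

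Day 570 lies outside the 18 months in 5.2.

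**Look-ahead, one woman.** Take fills on days 0 and 510. If she lives, her window is days 0 to 570. If she dies on day 200, her only fill is day 0, the window closes at day 60 and the death is not counted. Days 60 to 510, that is 510 − 60 = 450 days, are in the denominator but cannot contain a death.

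**Look-ahead, illustrative size.** The documents give no gap data, so all of the following are assumptions: 30-day fills, 6% stop after each fill, long gaps of 61 days plus an exponential time with mean 60, constant hazard λ and true HR 1. With E = min(last fill + 30, 540) and a window to E + 30:

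ratio = deaths counted from fills before death / (λ × person-time from full histories)

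Simulating 1,000,000 fill histories per scenario gives:

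| Fills before a long gap | Women with such a gap | Counted/true deaths | Mean days at risk |
|---|---|---|---|
| 2% | 16% | 0.96 | 372 |
| 4% | 29% | 0.93 | 377 |
| 10% | 54% | 0.84 | 390 |

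With no gaps the ratio is 1.00. Stopping the tail at day 540 instead of 570 changes little (0.962 v 0.963 at 2%; 0.840 v 0.844 at 10%).

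**Composite HR.** Assume that 20–60% of first events are not followed by a refill. With equal gap shares the HR is 1.00. It is 0.99–0.98 for 4% v 2% and 0.99–0.96 for 10% v 5%; with the arms reversed, 1.01–1.02 and 1.01–1.04.

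**Random error.** Scale the ACTIVE MACE proportions (0.5% and 0.6%, section 6.2.3) to 8,000 women per arm and the mean time at risk:

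- 8,000 × 0.005 × 372/540 = 27.6 events; CI factor exp(1.96 × √(2/27.6)) = 1.70
- 8,000 × 0.006 × 390/540 = 34.7 events; CI factor 1.60

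An HR shift of at most 4% is small beside a 95% CI that runs from the HR divided by 1.6–1.7 to the HR multiplied by it.

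**Planned sensitivity analyses.** Section 7.8.10 varies the caliper, restricts the population, replaces CV death by all-cause in-hospital death, or requires no diagnosis in the previous 183 days. None ends the window at a gap.

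**The case against.** The plan does contain a workable rule. Section 7.8.7 governs the safety analysis, 7.6.7.2 defines its end date, and 7.8.8 uses the same last fill plus supply. The 7.1 sentence may be meant only as a remark about gaps, since the same section makes safety as-treated. The 18 months plus 30 days in 7.1 and 7.8.9 point to a tail running to day 570, and censoring at window end is implied by a Cox model of on-treatment events. All this is fair, and it makes the repair one of wording. It does not remove the conflict: the tail still contradicts 5.2 and 7.8.3, and the 7.1 sentence names CV safety explicitly.

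The 12-consecutive-month restriction in 7.8.10.1 covers safety endpoints and, through 7.8.8, carries a 60-day gap limit. It bears on the gap rule only indirectly: it selects women and leaves the window unchanged, so gaps after month 12 are still bridged.

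Three stronger readings are tempting and should not be drawn:

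- Read literally, 7.8.3 ends at a fill date, so no CV death could ever count. That wording is probably loose, and 7.6.7.2 with 7.8.7 contradicts it.
- A reader might infer that the CV hazard ratio is biased. The planned measure is time to first event by Cox model, and the shifts above are within random error. Absolute frequencies enter only through the Kaplan-Meier sentence in the synopsis.
- The 65–68% capture of specialty and mail-order claims (7.5) might suggest large losses through apparent gaps. Those figures describe channels and are not per-fill probabilities. If misses were independent by fill, the ratio with the tail would be 0.92–0.93; if capture is all-or-none per woman, it is 1.00.

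**Conclusion.** The end-date conflict stands and should be fixed: 60, 30 or 540 days for a single assumed 30-day fill, depending on the section followed.

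The look-ahead follows from the gap rule itself and needs no assumption to exist. Its size does: 0.96 to 0.84 of true in-hospital CV deaths under the assumed fill patterns, and unknown in these data. It affects the Kaplan-Meier estimates of CV death more than any comparison, and it is minor.

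A distinct problem lies in 7.8.10.1. Requiring 12 months of exposure creates immortal time even with no gaps. With 30-day fills, 360 days of exposure needs a fill at about day 330 (360 − 30), so no earlier death can be counted. This is not a consequence of bridging gaps.

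**What to change.** 1. Use one end date in 5.2, 7.1, 7.6.7, 7.8.3 and 7.8.7: the 7.6.7.2 date, with exposure cut at day 540, plus the 30 days of 7.8.7. Align the 18-month limit in 5.2 with the 18 months plus 30 days in 7.1 and 7.8.9. Confine the 7.1 sentence on 18-month follow-up regardless of gaps to effectiveness. State that women without a CV event are censored at that date or at in-hospital non-CV death.
2. Add one prespecified sensitivity analysis of the CV endpoints, ending follow-up at the end of supply before the first gap over 60 days (the 7.8.8 limit) plus a stated tail. A 60-day tail gives a ratio of 1.00; a 30-day tail gives 0.98 if a further 10% of fills precede gaps of 1–60 days. Report gap frequency by arm. An analysis over the full 18 months is optional.
3. Do not interpret the 12-month exposure restriction as a check on CV death.

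The cost is wording, one derived date and one extra run. The gap-limited run is less precise: with a 60-day tail, mean days at risk are 354 v 372 (−5%), 319 v 377 (−15%) and 245 v 390 (−37%) at gap shares of 2%, 4% and 10%. It may also treat an uncaptured fill as a gap and may censor informatively, so it should remain a sensitivity analysis. Table 3 dates the data extraction to June 2021, so the window should be settled in writing before CV results are seen.
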